### B. Subsidiary Objectives:

The subsidiary objectives of the Registry are:

1. To study cardiovascular mortality at one, three and five years globally and after stratification according to symptoms, etiology of disease, ejection fraction and chest X-ray findings in the above populations.

2. To study morbid events at one year in the above population.

3. To relate other baseline covariates of prognostic importance to subsequent mortality and morbidity in the above population.

4. To characterize in greater detail clinical characteristics, echocardiographic abnormalities, arrhythmia status, functional capacity and neurohumoral levels and to correlate these detailed findings with subsequent mortality and morbidity in a stratified randomly selected sample of 1000 patients from among the patients entering the Registry.

5. To compare baseline characteristics and follow-up events of this relatively unselected population with those of the SOLVD Trials.

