## VI. STUDY SIZE

It is expected that over 6,000 patients will be recruited into the Registry during the specified nine-month time period. In order to avoid a predominance of ischemic heart disease, special attempts to include patients with other etiologies may be required. These categories include the following:

- 1) Valvular heart disease with EF  $\leq$  45%
- 2) Primary diagnoses of idiopathic cardiomyopathy and active myocarditis.

3) Unusual and specific causes, such as amyloidosis, hemochromatosis, hypertrophic hyperdynamic cardiomyopathy (so-called IHSS), diabetic cardiomyopathy, alcoholic cardiomyopathy, etc.

The period for collecting such unusual cases may be extended beyond the first nine months Registry collection and as long as 1991. A decision regarding that will be made after the first nine months of recruitment.

The calculations in Table 1 examine the statistical power attained for comparing the mortality rates between two subgroups from the 6000 SOLVD Registry patients, under various assumptions. Comparisons of mortality rates can be done asymptotically with the test of difference of two binomial proportions (Rosner, p. 325). A two-sided test with a 0.05 level of significance is thus considered.

The following examples aid in the interpretation of the calculations in Table 1.

Case 1 would be for testing the difference in mortality between, for example, those with EF ≤ .40 (75% of Registry) vs. those with EF > .40 (25% of Registry). Power for this case is virtually unity.

Cases 2-3 and 4-6 look at testing the different mortality rates in a very rare subgroup vs. the entire rest of the Registry, under different relative risk situations. The rarer the etiology, the higher the relative risk needs to be, but a RR of 2 or greater has sufficient power to be detected, even after only one year. The power is greatly improved after three years.

Cases 7-9 look at testing the different mortality rates between two very rare subgroups, one that is seen in 2% of the patients vs. one that is seen in 1% of the patients. Informal estimates of prevalence of different etiologies suggest that amyloidosis would be seen in 20 per 1000 patients (2%), hemochromatosis would be seen in 10 patients per 1000 (1%), diabetic cardiomyopathy in 6-8%, alcoholic cardiomyopathy in 7-10%, post-partum in 2%. These cases need three years' worth of data to be tested with reasonable power, even with a relative risk of 2.

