Cases 10-11: With 6000 persons in the Registry, it is not unreasonable to expect roughly 1000 patients with idiopathic cardiomyopathies. If this group is divided by tertiles of EF into low, intermediate and high EF, one would like to compare the mortalities between the high EF group and the low EF group. Assuming a relative risk of 3 provides power close to 1, while with a relative risk of 2, the power is virtually one at the three-year comparison.

				One-ye	ear		Power
Case #	n	m	pl	p2	RR	@1-year	@3-year
1	4500	1500	.12	.05	1/2.4	1.00	1.00
2	5900	100	.12	.24	2.0	.90	1.00
3	5900	100	.12	.18	1.5	.45	.77
4	5950	50	.12	.24	2.0	.69	.94
5	5950	50	.12	.30	2.5	.86	1.00
6	5950	50	.12	. 36	3.0	.99	1.00
7	120	60	.20	.30	1.5	.33	.58
8	120	60	.20	.40	2.0	.81	.97
9	120	60	.12	.24	2.0	.54	.87
10	333	333	.05	.15	3.0	.99	1.00
11	333	333	.06	.12	2.0	.77	.99

Table 1 One-year and three-year power for comparison of mortality rate between various Registry subgroups

Key: n = sample size in first subgroup m = sample size in second subgroup pl = 1-year mortality rate in first subgroup p2 = 1-year mortality rate in second subgroup RR = relative risk of second to first subgroup Thus, it is clear from the above examples that a sample size of 6000 patients in the Registry is quite adequate for comparison of mortality rates between various subgroups, especially after three years but in several cases even after one year.

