If the participant is acknowledged to be alive and has not required any hospitalization during the preceding year, no further information will be required at this time beyond completion of the One-Year Follow-up form. If the participant has died, the research nurse will obtain reports of hospitalizations, if any have occurred, and circumstances of death as well as the death certificate, and will forward a Designation of Death form, the Death Certificate Cover Sheet form, and Hospitalization forms (as needed) promptly to the Coordinating Center. If the participant is living but has required one or more hospitalizations during the preceding year, the nurse will obtain reports of the hospitalizations, and will complete the Hospitalization form for each hospitalization. (Copies of these forms are included in appendix B.)

It should be noted that if a participant is registered in the logbook at a participating center and subsequently dies during the same hospitalization, the center is required to seek his/her eligibility for the SOLVD Registry and to complete and submit to the Coordinating Center the Main Registry Baseline form, the Designation of Death form, and the Death Certificate Cover Sheet for this participant.

There will be a time allowance of 60 days for submitting the one-year follow-up forms to the Coordinating Center, i.e., 60 days after the anniversary of enrollment.

The second type of information derived from the follow-up of the Registry participants will be a long-term ascertainment of vital status through the National Death Index (NDI) and corresponding registries in Canada and Belgium. Although several matching criteria are available for searches of the NDI, the three absolutely essential identifiers include the social security number, the date of birth and the full name of the participant. Information on vital status will be sought approximately two years and four years after enrollment of a patient in the Registry. For the United States, this will be done at the SOLVD Coordinating Center. The Canadian centers and the Belgian center will be responsible for collecting these data from their respective Bureaus of Vital Statistics and for submitting them, upon request, to the SOLVD Coordinating Center.

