#### Endpoint Data

The follow-up endpoints will provide two sets of information. The first set will be one-year information on vital and on major non-fatal cardiovascular events, including recurrent and/or new complications requiring hospitalization such as worsening of functional status, myocardial infarction, stroke, pulmonary complications, severe serious arrhythmias, drug toxicity, and cardiac surgery--including cardiac transplantation. The second set of endpoint data will provide long-term ascertainment of vital status, approximately two years and approximately four years after enrollment in the SOLVD Registry.

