### X. STATISTICAL ANALYSIS

The primary outcome is all-cause mortality. Thus, the main variable for analysis will be the time from entry into the Registry until death. Cardiovascular mortality as well as other causes of death will be examined from major categories of the underlying cause of death from the death certificate. The analysis of the major outcome of death will involve the use of the proportional hazards model (Cox, 1972). This analysis will allow for the adjustment of baseline covariates thought to be of prognostic importance; for example, ejection fraction, age, sex, race, etiology. Similarly, analyses will be conducted for morbid events. A careful evaluation of the suitability of the proportional hazards assumption will be conducted as part of these analyses. In addition, the relationship of the echocardiographic and Holter variables to prognosis (collected systematically on the 1000 patients) will be assessed. The data will be analyzed separately in a number of subgroups based on etiology, sex, age, functional class, etc.

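### Cardiovascular mortality is an objective at three and five years, but the protocol describes no step that would collect cause of death after the one-year follow-up

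*Protocol*

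**What the plan says.** **Objective.** Protocol Section II.B, item 1: "To study cardiovascular mortality at one, three and five years globally", and also by symptoms, etiology, ejection fraction and chest X-ray findings.

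**Source of cause.** Section X examines cardiovascular and other causes of death using the "underlying cause of death from the death certificate". It sets no time limit on this.

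**Collection up to one year.** In Section IX, Follow-up Data, when a participant is found at the one-year follow-up to have died, the research nurse obtains the certificate and the circumstances of death. The nurse then sends the Designation of Death form and the Death Certificate Cover Sheet to the Coordinating Center. A separate paragraph requires both forms for patients who die in the hospitalization during which they were logged.

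**Collection after one year.** The same section says the second type of follow-up information "will be a long-term ascertainment of vital status through the National Death Index (NDI) and corresponding registries in Canada and Belgium", sought at about two and about four years after enrollment. The Endpoint Data paragraph agrees: "The second set of endpoint data will provide long-term ascertainment of vital status". The Introduction and the Section VIII timetable entries for Years 3 and 5 likewise mention vital status only.

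**The concern.** The objective and the analysis section need a cause for every death up to five years. The data-collection section defines what the later data set contains, and cause is not in it. The later searches are assigned to the Coordinating Center for the United States and to the Canadian and Belgian centers for their own countries. Each is asked for vital status, and nobody is asked to request certificates.

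This goes beyond detail left for an analysis plan. It concerns a collection step that the protocol spells out for early deaths and omits for later ones. If centers follow the text, the later data set alone cannot yield three- and five-year cardiovascular mortality, overall or by stratum. If some centers request certificates on their own initiative and others do not, completeness of cause would differ by country or center.

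**Working it through.** The protocol gives no share of deaths lacking a cause, so the check estimates how many deaths fall after the point where cause collection is described.

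**Inputs**
- Size: 6,000, from Section VI ("It is expected that over 6,000 patients will be recruited into the Registry during the specified nine-month time period").
- One-year mortality: 0.12, the first-subgroup rate in cases 1–6 and 9 of Table 1, whose key reads "pl = 1-year mortality rate in first subgroup". It is a planning value for subgroups, not a stated Registry-wide rate.
- Hazard after year one: not stated. Constant hazard is assumed and tested below against Table 1.

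**Does constant hazard fit the plan's own figures?** Section VI compares subgroups "asymptotically with the test of difference of two binomial proportions", and "A two-sided test with a 0.05 level of significance is thus considered". I took each three-year rate as P = 1 − (1 − p)³ and used the pooled-variance power formula without continuity correction:

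power = Φ{[|P₁ − P₂| − 1.96·√(P̄(1−P̄)(1/n + 1/m))] / √(P₁(1−P₁)/n + P₂(1−P₂)/m)}

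For case 3 (n = 5,900, m = 100, p = 0.12 and 0.18):
- P₁ = 1 − 0.88³ = 0.3185 and P₂ = 1 − 0.82³ = 0.4486, a difference of 0.1301.
- The null standard error is 0.0471 and the alternative standard error 0.0501.
- (0.1301 − 1.96 × 0.0471)/0.0501 ≈ 0.755, so power is 0.775. Table 1 states .77.

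All 11 three-year powers are reproduced within two points. (In the one-year column 10 of 11 are. Case 5 gives .915 against .86, a separate matter that does not bear on this point.) Constant hazard is therefore consistent with the plan's working.

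**Deaths after year one.** Cumulative mortality is 1 − 0.88^T, and the share after year one is 1 − 0.12/(1 − 0.88^T). Year-one deaths: 6,000 × 0.12 = 720.

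| T (years) | Mortality | Deaths of 6,000 | After year one | Share |
|---|---|---|---|---|
| 3 | 0.319 | 1,911 | 1,191 | 62.3% |
| 4 | 0.400 | 2,402 | 1,682 | 70.0% |
| 5 | 0.472 | 2,834 | 2,114 | 74.6% |

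**Sensitivity of the five-year share**
- Other rates, constant hazard: 77.9% at 0.05, 67.8% at 0.24, 56.6% at 0.40.
- Case 1 mix (75% of patients at 0.12, 25% at 0.05): one-year mortality 0.1025, five-year 0.411, share 1 − 0.1025/0.411 = 75.0%.
- Hazard falling after year one, with p = 0.12, h = −ln 0.88 and five-year survival 0.88·exp(−4kh): 70.0% for k = 0.75, 62.3% for k = 0.50, 53.2% for k = 0.33. The three-year shares are then 56.1%, 46.8% and 37.2%.

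**Search times.** For patients entering on 1 January 1988, the timetable windows (December 1989 to November 1990, and December 1991 to November 1992) fall 1.92–2.91 and 3.92–4.91 years after entry. For those entering on 30 September 1988 they fall 1.17–2.17 and 3.17–4.17 years after entry. Neither window reaches three or five years for anyone enrolled in the nine-month period.

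**The case against.** A reader might infer that later deaths will have no cause and that the objective cannot be met. The documents do not support that much, for four reasons.

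- Section X names the certificate as the source of cause without confining it to year one. The Registry Death Certificate Cover Sheet and Designation of Death form in Appendix B show no such limit in their legible text.
- The protocol does not say what a match in the National Death Index or in the Canadian or Belgian registries returns. It could include a coded cause or lead to a certificate, so neither answer can be assumed.
- Section III commits centers to following their patients throughout the study, and the baseline form mentions a Manual of Operations that is not available here. A retrieval step could be set out there.
- Section III expects at least 20% of Registry patients also to be in the SOLVD trials, whose records might hold a cause. The protocol describes no transfer of later trial deaths. If 20% were covered and had the same mortality, 0.8 × 74.6% ≈ 60% of five-year deaths would still lack a described route.

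A reader might also infer that a Cox model for cardiovascular death is compromised. Section X applies the Cox model to the major outcome of death, with all-cause mortality primary, and says only that cardiovascular mortality will be examined. No such cause-specific model is expressly specified.

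These points limit the consequence but leave the gap. Naming a certificate in the analysis section does not arrange its collection, and every description of follow-up after year one is confined to vital status.

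**Conclusion.** The point stands as an internal mismatch. Sections II.B and X require cause of death to five years. Sections VIII and IX collect only vital status after year one, so later deaths have no described route to a cause. That is weaker than saying a cause will be missing.

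The deaths concerned are about 62% of those by three years, 70% by four and 75% by five. These shares rest on 12% one-year mortality and a constant hazard. Three quarters is not a fixed figure: the five-year share was about 53% to 78% over the assumptions tried, and still more than half at the low end.

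The cause-of-death gap affects one subsidiary objective at its later time points and leaves all-cause mortality untouched. The related mismatch in search times also affects the primary objective, because all-cause mortality is wanted at three and five years. It means that adding cause of death alone would not deliver the later cardiovascular results.

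**What to change.** 1. In Section IX (Follow-up Data and Endpoint Data) and the Section VIII timetable, state that for every death found in the National Death Index, Canadian or Belgian searches, the death certificate or the coded underlying cause will be obtained. Record it on the existing Registry Death Certificate Cover Sheet, and say who makes the request in each country. The Section X definition then applies in all years.
2. Align the search times with the three- and five-year objectives, so that each search covers all deaths up to the time point for every patient.
3. If this is not affordable, limit subsidiary objective 1 to one-year cardiovascular mortality.

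**Cost.** Under the 12% and constant-hazard assumptions, certificate or cause-code requests would be needed for about 1,700 deaths after year one with a last search at four years, or about 2,100 at five years. Later searches also postpone the final analysis. Limiting the objective adds no collection cost but gives up the later cardiovascular results.

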Appendix B: Forms

## Appendix C: Protocols for Substudy Procedures

Appendix D: Stratification for Substudy Participants

### I. INTRODUCTION

The patients entering the SOLVD trials are likely to represent an uncertain subset of the total population of patients with heart failure or left ventricular dysfunction at the participating clinical centers. The trial population is expected to be truncated with patients having the worst and best ventricular function excluded from the trials. Patients whose ventricular dysfunction or heart failure is related primarily to diastolic abnormalities without systolic dysfunction are excluded from the SOLVD trials, since marked systolic dysfunction is the key entry criterion. Other interesting and important subsets of patients, such as those with pulmonary edema at entry, are likely to be underrepresented in the SOLVD trials. In order to study the clinical course of a broader and more representative group of consecutively collected patients with heart failure at participating institutions and the relationship(s) of the SOLVD trial participants to this larger and less selected sample, a Registry of patients with left ventricular dysfunction will be developed. Vital status and clinical events will be determined at one year by a written questionnaire or telephone follow-up; longer term vital status will then be determined by periodic search of national death registries.

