### II. AIMS OF THE REGISTRY

### A. Primary Objective:

The primary objective of the Registry is to study all-cause mortality at one, three and five years in a large (approximately 6,000) consecutive and relatively unselected cohort of patients with heart failure and/or with left ventricular dysfunction. The patients will be stratified according to symptoms, etiology of disease, ejection fraction and chest X-ray findings at entry into the Registry.

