### Follow-up Data

Two types of follow-up information will be obtained. First, a one-year follow-up questionnaire requesting information on vital status and hospitalizations will be administered by mail and followed, if necessary, by a telephone contact.

The one-year follow-up interview is to be attempted through the mailing of a letter that will be standard and ask the following questions on an attached form (SOLVD REGISTRY "FOLLOW-UP FORM"):

i) Have you been hospitalized during the period \_\_\_\_\_\_\_ to ? If yes, please give us the name of the hospital(s), date(s) of hospitalization(s) and the reasons for the hospitalization(s). [Note that all hospitalizations are of interest. The dates to be filled in by the clinic should reflect a one-year time period from their date of enrollment into the Registry.]

ii) Are there any other matters about your health that are concerning you? [This question will not be included in the collaborative data base.]

iii) Question number 35 of the Quality of Life form (the "ladder of life").

The body of the letter will be uniform across centers, but may contain center-specific paragraphs to continue participant rapport. The participant will be asked to complete the form with the above questions and return it. Some of the data on the form will be entered on the SOLVD REGISTRY "ONE-YEAR FOLLOW-UP INTERVIEW COVER FORM."

If contact is not established through the mail, phone calls and other means of establishing contact are to be attempted. The form can be completed over the phone.

If the participant is participating in the SOLVD trials, DO NOT attempt a mail or phone contact by the Registry. Contact information is to be obtained from the closest scheduled SOLVD trial visit occurring after one year from the SOLVD REGISTRY BASELINE FORM. Since the "ladder of life" will not be available, it must be administered at a visit close to the one year time and the code entered on the SOLVD Registry "Follow-up Form."

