### Appendix A

### A1: SOLVD REGISTRY FLOW DIAGRAM

.4

			19
	SOLVD	REGISTR	
	BASEL	NE FORM	
	11/1	1/87	
REGISTRY ID:	FOR	i: R B F VERS	SION: A VISIT: 0
INSTRUCTIONS	This form is to be completed on all consecut using only the information available from the To be eligible for the Registry, the patient a diagnosis of congestive heart failure configuration Please print clearly when entering a response eral Instructions for Completing Forms for com-	a appropriate medical reco must either have an EF <= firmed by radiologic eviden te into the boxes. See the	rds. 45% or have hce.
	· •		
	SOLVD MAIN REGISTRY BASELINE FORM	(screen 1 of 15) (RBF pag	e 1 of 8)
A. IDENTIFY	ING INFORMATION	B. ELIGIBILITY ASSESSMEN	T Unrec
1.1 Today's	Date:/ // // /	
 
Most recently measur (should be 7 or more diac surgery, FTCA,
 
	ed Ejection Fraction days after an MI, car- or balloon valvuloplasty):
1.2 Initial	s of person completing form:	3.1 Percentage:	
2.1 Last Nam		3.2 Date://	Day / The Year
2.2 First N		3.3 Hethod utilized:	Radionuclide R Contrast angiography A 2-D echo E
2.3 Middle 1	Initial:		Not on chart U

2 (1.1. 1) (1.1. 1) (1.1. 1) (1.1. 1)

• .

•

				1			
	Yes	No l	Inrecorded	c.	DEMOGRAPHIC INFORMATION		
4.1	Primary diagnosis of heart failure and chest X-ray consistent with heart failure (X-ray should be 7 or			6.	Sex:	Male Female	M F
	more days after an MI, cardiac surgery, PTCA, or balloon valvuloplasty) Y	N	υ	7.	Ethnic Identity	American Indian	1
1. 9	Date of multiplan Y-news					Asian	2
4.4	Date of qualifying X-ray:					Black	3
	Month Day Year					Caucasian	4
53 1000				1		Hispanic	5
5.	Reasons for exclusion from Registry					Other	6
5.1	Presence of non-valvular congenital heart disease Y	N	U			Not on chart	7
5.2	Presence of any non-cardiac life- threatening disease which is unlikely to allow the patient to survive one year (Includes 11, 12, 13, 17, 18, 21 and 23 of SOLVD trials)	N	υ	8.	Date of Birth:	Year	
5.3	No telephone or reliable means of contact/follow up Y	N	υ	9.	Social Security Number (Ca (IMPORTANT!! MUST BE COMPL		):
5.4	Failure to consent to Registry Y	N	U		-	-	
5.5	Is patient eligible for Registry? Y (If NO, exit form)	N				Bagan antanan da na vindu na	-

SOLVD MAIN REGISTRY BASELINE FORM (screen 3 of 15) (RBF page 2 of 8)

10.1 Participant Street Address:	10.5 Zip Code/Canadian or European Postal Code:
	11. Participant Telephone Number (Home):
	HOSPITAL INFORMATION
10.2 City:	12.1 Hospital name:

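### Vital status after the one-year contact rests on death-registry matching alone, with no check of match completeness, so later mortality may be understated by an unknown amount

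*Protocol*

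**What the plan says.** Section II.A sets the target: "The primary objective of the Registry is to study all-cause mortality at one, three and five years", in about 6,000 patients.

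Section IX, Follow-up Data, describes two methods of ascertainment.

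- **At one year.** A questionnaire "will be administered by mail and followed, if necessary, by a telephone contact". Other means of contact are tried if these fail, and trial participants are covered through a trial visit. For a patient who has died, the nurse obtains the death certificate.
- **Afterwards.** The Introduction says that "longer term vital status will then be determined by periodic search of national death registries". Section IX places the searches at about two and four years after enrolment. The Coordinating Center searches the National Death Index for US patients; the Canadian and Belgian centers query their own bureaus. For the index, "the three absolutely essential identifiers include the social security number, the date of birth and the full name of the participant".

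The Registry Baseline Form in the appendix collects name, date of birth and social security number, and flags the last with "IMPORTANT!! MUST BE COMPL" (the line is cut off in the extracted text). Section III asks centers to commit to following their patients for the whole study, but no contact procedure after year one is described. Section III also expects at least 20% of Registry patients to be in the SOLVD trials. Subsidiary objective 5 compares Registry patients with those of the trials. Section X plans a Cox model and adds: "A careful evaluation of the suitability of the proportional hazards assumption will be conducted as part of these analyses".

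**The concern.** A registry search finds deaths; it does not confirm survival. A patient who died but was not matched, because an identifier was wrong or missing or because the death lies outside the registry searched, looks the same as a patient who is alive. At one year someone tries to reach each patient, so a death can come to light without any matching. Later the match is the only route described.

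The method of ascertainment therefore changes inside the primary outcome, and nothing in Section IX would show how complete the second method is. At stake are the level of three- and five-year mortality and, if some groups keep a second source of information, comparisons between those groups. The clearest such case is objective 5: if trial follow-up feeds Registry vital status after year one, trial participants have two sources and the other patients one. The protocol does not say whether it does.

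**Working it through.** **Inputs from the protocol.** One-year mortality .12 (Section VI, Table 1, first subgroup in cases 1–6 and 9); 6,000 patients; at least 20% in the trials; minimum 300 patients per center (Section III, for twenty centers).

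**Input not in the protocol.** Match sensitivity *s*, the share of later deaths that the searches find. It is assumed, over .90 to .98.

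**Step 1. The plan's own later figures.** Table 1 gives three-year powers. Taking three-year risk as 1 − (1 − p)³ in the two-sided 5% test of two proportions, with pooled variance under the null, reproduces all eleven within .02 (case 3: .775 against .77; case 9: .881 against .87). Table 1 is thus consistent with constant hazard and complete ascertainment, so the same hazard assumption is used here.

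**Step 2. True mortality.** With S(1) = .88:
- three years: 1 − .88³ = 1 − .6815 = 31.9%
- five years: 1 − .88⁵ = 1 − .5277 = 47.2%

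**Step 3. Observed mortality if unmatched deaths are counted as survivors**, with year-one capture complete: observed(3) = .12 + *s* × (.88 − .6815) = .12 + *s* × .1985. Deaths missed = 6,000 × (1 − *s*) × .1985. The apparent hazard in years 1–3 relative to year 1 is {−ln[(1 − observed(3))/.88]/2} / {−ln(.88)}.

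| *s* | Observed 3-year mortality | Deaths missed by 3 years | Apparent hazard, years 1–3 vs year 1 (truth 1) |
|---|---|---|---|
| 1.00 | 31.9% | 0 | 1.00 |
| .98 | 31.5% | 24 | .98 |
| .95 | 30.9% | 60 | .94 |
| .90 | 29.9% | 119 | .89 |

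Each 5 points of lost sensitivity cost about 1.0 point of three-year mortality. Carried to five years, *s* = .95 would give 45.5% against 47.2% and 106 missed deaths. That supposes a search complete to five years, whereas the last search in the timetable (December 1991 to November 1992) falls about 3.2 to 4.9 years after enrolment in January to September 1988. The three-year figures are therefore the ones to use.

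**Step 4. Does the hazard have to appear to fall?** Let year-one capture be incomplete as well, at *s*₁, with *s*₂ afterwards: observed(1) = .12*s*₁, observed(3) = .12*s*₁ + .1985*s*₂.
- .95 then .95: ratio .99
- .95 then .90: ratio .93
- .90 then .95: ratio 1.04, a slight rise
- If the two-year search also recovers year-one deaths missed by contact, and misses are independent, the last case becomes *s*₁ = 1 − .10 × .05 = .995, with ratio .95.

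The direction depends on quantities that the protocol does not give.

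**Step 5. Effect on comparisons.**
- Uniform loss: Table 1 case 2 (.12 against .24) with *s* = .90 in both groups. The three-year risk ratio moves from 1.76 to 1.77, and the hazard ratio for years 1–3 from 2.15 to 2.11. Power for case 3 goes from .775 to .743.
- Differential loss: two groups with the same true 31.9%, one fully captured and one at *s* = .95, show 31.9% against 30.9%, and an apparent hazard ratio of 1/.943 = 1.06 in years 1–3.

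**Step 6. How well could sensitivity be measured?** Known year-one deaths: 6,000 × .12 = 720. At a true sensitivity of .95, SE = √(.95 × .05/720) = .008. A center with 300 patients would have 36 such deaths: SE = √(.95 × .05/36) = .036.

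**The case against.** The case on the other side has real force.

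- **No match loss is shown.** Correct. The sizes above are a range under an assumed sensitivity. The form treats the social security number as compulsory, so missing identifiers may be few; wrong identifiers and deaths outside the searched registries remain possible.
- **Year-one contact is not perfect either.** Correct. A reader might infer that the change of method creates a false fall in hazard at one year. Step 4 shows that this requires later capture to be worse than year-one capture, which the documents do not establish.
- **The Cox model is hardly touched by a uniform loss.** Correct. It leaves the baseline hazard free, so a common drop in capture alters the baseline and barely moves hazard ratios (Step 5). A reader might infer that the planned check of proportional hazards would be corrupted; that needs capture to differ between the groups compared.
- **Country differences.** Searches are run differently by country, but no comparison across countries is among the objectives or in Section X.
- **Analysis rules belong in an analysis plan.** Partly. The protocol nowhere writes that unmatched patients count as alive; that is an inference, and the handling of such patients could be set in a plan not shown here. Who is submitted to the searches is a matter of data collection, fixed in Section IX and hard to recover later.
- **Centers commit to follow patients throughout.** They do, but no procedure after year one gives that commitment effect.

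**Conclusion.** The concern holds in a conditional form. After the one-year contact, registry matching is the only described source of vital status, and nothing measures its completeness. Mortality after year one may be understated by an amount that cannot be estimated from the data as planned. Under 12% one-year mortality, constant hazard, complete year-one capture and unmatched deaths counted as survivors, the three-year understatement is about 0.4, 1.0 or 2.0 percentage points at sensitivity .98, .95 or .90.

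Within-Registry comparisons by etiology or ejection fraction are little affected if the loss is uniform. The main comparative risk is objective 5, and only if trial follow-up supplies Registry vital status after year one. This is worth correcting because the remedy is cheap and must be in place when the searches are submitted.

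**What to change.** In Section IX, Follow-up Data:

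1. Submit all enrolled patients to the planned searches, including deaths already known from the one-year contact (about 720 at 12%) and from trial follow-up.
2. Estimate match sensitivity from those known deaths, pooled (SE about .008 at .95), and by country only where numbers allow (SE about .036 with 36 deaths).
3. State whether trial follow-up contributes to Registry vital status after year one.
4. Censor patients lacking the essential identifiers at last contact instead of counting them as alive.
5. Report later mortality uncorrected, with a sensitivity analysis corrected for the estimated match rate.

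The cost is several hundred more names in searches that are already planned, one further analysis, and slightly wider intervals for the corrected estimates. Sensitivity measured on year-one deaths carries over to later deaths only if identifiers and registry coverage are similar, and the report should say so.
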